5.2.2 Discontinuation of Study Vaccine (Participant)

A participant may not receive additional study vaccine administrations for any of the reasons outlined in Section [5.1.5](#).

Additional reasons for discontinuation of study vaccine for a participant would include:

- Participant request to discontinue study vaccinations.
- Participant is lost to follow-up.
- New information becomes available that makes further participation unsafe.
- Termination of the trial study vaccinations.

Should study vaccine administration be discontinued, the participant will be encouraged to continue study participation for study evaluations through Day 394 (Final Visit).

5.2.3 Withdrawal/Discontinuation from the Study

Participants are free to withdraw from participation in the study at any time upon request, without prejudice to further treatment the participant may need to receive. The investigator will request that the study participant complete all study procedures pending at the time of withdrawal.

A participant will be recorded as a screen failure for the study if any of the following occur **prior to** first administration of study vaccine:

- Eligibility criteria are not met.
- The participant requests to discontinue study participation.

If, after randomization, a participant withdraws from the study, an EOS eCRF will be completed and information related to the withdrawal will be documented in the eCRF. The investigator will document whether the decision to withdraw a participant from the study was made by the participant or by the investigator, as well as which of the following possible reasons was responsible for withdrawal:

- Lost to follow-up
- Death
- Study terminated by Sponsor
- AE or SAE (specify)
- Participant request (specify)
- Protocol deviation (specify)
- Physician/Investigator decision (specify)
- Pregnancy
- Other (specify)

The investigator must capture the reason for withdrawal from the study in the eCRF for all participants that withdraw.

If, after enrollment, a participant desires to withdraw from the study because of an AE, the investigator will try to obtain agreement to follow-up with the participant until the event is considered resolved or stable and will then complete the EOS eCRF.

If a participant approaches the site requesting to receive off-study COVID-19 vaccine, the participant should be counseled and reminded of the Switchover study design (for Phase 1, 2, 3a and 3b cohorts) or the comparison with another active vaccine (for Cohort 3c) whereby all participants will receive active investigational vaccine. The participant should be encouraged to demonstrate evidence of a scheduled appointment to receive off-study COVID-19 vaccine. If, after counseling and confirmation of the appointment, a study participant maintains his/her interest in receiving off-study vaccine, he/she will be advised to preferably schedule off-study vaccine at least 28 days after last dose of study vaccine, the participant will not be eligible to receive Switchover/Further Study Vaccine vaccine (if the Switchover/Further Study Vaccine day has not passed) and the participant is asked to continue study procedures through Final Visit (Day 394).

If a participant withdraws from the study, he/she may request destruction of any remaining samples taken and not tested, and the investigator must document any such requests in the site study records and notify the Sponsor or CRO accordingly.

If a participant withdraws consent and specifies no further contact with him/her or persons previously authorized by the participant to provide this information, this should be documented by the investigator in the study source documents. If vital status (whether the participant is alive or dead) is being measured, publicly available information should be used to determine vital status only as appropriately directed in accordance with local law.

5.2.4 Discontinuation of Study Dosing (Study-wide)

All cases of severe COVID-19, SAEs determined to be related to study vaccine or deaths determined to be related to study vaccine will be referred to the DSMB (Section 8.10.3) in an expedited fashion.

In the event of death determined to be related to study vaccine, further vaccination will be paused until the relevant safety data has been reviewed by DSMB.

The DSMB, based on their review of the blinded or unblinded safety data (including assessment for potential vaccine-associated enhanced respiratory disease [VAERD]) will recommend whether the study should terminate, proceed unmodified, or proceed but with changes to the protocol.

Although the Sponsor has every intention of completing the study, the Sponsor reserves the right to discontinue the study at any time for clinical or administrative reasons.

5.3 Lost to Follow-Up

A participant will be considered lost to follow-up if he or she fails to return for scheduled visits or is unable to be contacted by the study site.

The following actions must be taken if a participant fails to return to the clinic for a required study visit:

- The site must attempt to contact the participant and reschedule the missed visit as soon as possible and counsel the participant on the importance of maintaining the assigned visit schedule and ascertain whether the participant wishes to and/or should continue in the study.
- Before a participant is deemed lost to follow-up, the investigator or designee must make every effort to regain contact with the participant (where possible, 3 telephone calls and, if necessary, a certified letter to the participant's last known mailing address or local equivalent methods). These contact attempts should be documented in the participant's medical record.

If the participant continues to be unreachable, he/she will be considered to have withdrawn from the study at the date of last study contact.

5.4 Replacement of Participants

Participants who withdraw from the study after randomization will not be replaced.

6 STUDY TREATMENTS

6.1 Method of Assigning Participants to Study Groups

Assignment of participants to Study Groups will proceed using an IRT system. The site personnel (study coordinator or specified designee) will be required to enter or select information including but not limited to the password, the protocol number, participant age and the participant code (a unique number identifying the participant), and participant's relevant underlying health conditions that will be used to determine "at risk" status prior to randomization. The site personnel will then be provided with a vaccine assignment. The IRT system will provide an unblinded confirmation report containing the participant code and study intervention allocation assigned. The confirmation report must be stored in the site's unblinded files away from the view of blinded site staff.

Participants will then be randomly assigned and stratified as described in Section 4.5.2. Treatment designation will be assigned in the IRT.

Confirmation of a participant's eligibility to receive additional study vaccine must be entered into the IRT prior to dispensing the assigned vaccination on Day 92.

6.2 Study Vaccine Manufacturer

For Phase 1, 2, 3a and 3b ARCT-154 and placebo (0.9% sterile saline) constitute the study vaccine.

For Phase 3c ARCT 154 and the Astra Zeneca vaccine ChAdOx1 constitute the study vaccines.

Arcturus Therapeutics, Inc. ([name]), as owner of the drug product, is the designated manufacturer of ARCT-154. Arcturus contracts manufacture of ARCT-154 as follows:

- [REDACTED]
- [REDACTED]
- [REDACTED]

0.9% saline and ChAdOx1 are sourced from commercial supply and emergency use supply (in Vietnam), respectively and manufacturer details can be found in the prescribing information.

6.3 Study Vaccine, Dosage, and Route of Administration

The ARCT-154 study vaccine is a lipid-nanoparticle-formulated RNA product. The RNA comprises a replicon based upon an alphavirus in which RNA coding for the virus structural proteins has been replaced with RNA coding for the SARS-CoV-2 S glycoprotein containing the D614G variant mutation.

The nanoparticle composition includes 4 lipid excipients (ionizable cationic lipid, Arcturus proprietary lipid; neutral lipid, 1,2-distearoyl-sn-glycero-3-phosphocholine; cholesterol; and polyethylene glycol-lipid conjugate).

ARCT-154 is provided as a lyophilized formulation in a 12-mL-size glass vial presentation that allows for multiple 5.0- μ g doses of ARCT-154 after reconstitution. The diluent for reconstitution consists of sterile 0.9% sodium chloride for injection, that is USP, BP or equivalent grade, and is preservative-free.

The comparator (placebo) for Phase 1, 2, 3a and 3b is sterile 0.9% sodium chloride for injection that is United States Pharmacopeia (USP), British Pharmacopeia (BP) or equivalent grade, and is preservative-free.

The comparator for Phase 3c is the Astra Zeneca vaccine ChAdOx1, which is already authorized for use in Vietnam. ChAdOx1 active substance is a chimpanzee Adenovirus encoding the SARS-CoV-2 Spike glycoprotein. Further details can be found in the prescribing information for ChAdOx1.

The study vaccines will be prepared by an unblinded trained site staff member in accordance with the Pharmacy Manual, and outside of the view of blinded team members. Study vaccines will be matched for volume (0.5 mL) and appearance (1-mL syringe) prior to administration. Study vaccine will be administered by IM injection to the deltoid muscle by an unblinded health care provider who will not be involved in assessments of any study endpoints.

Study vaccine preparation and administration should be performed in an area outside of the view of blinded team members. All documents containing unblinded information must also be kept out of view of the blinded team members and the study participants. Unblinded team members will not otherwise participate in other study-related procedures or assessments of the participant.

The IM injection of the study vaccine will be into the lateral aspect of the deltoid muscle of the non-dominant arm, where possible.

Epinephrine for subcutaneous (S.C.) injection, diphenhydramine for intravenous injection, and any other medications and resuscitation equipment for the emergency management of anaphylactic reactions must be available in close proximity to the room where the vaccination is administered.

See Section 4.5.3.2 for additional guidance on procedures during the Dose Administration visit.

6.4 Management of Clinical Supplies

6.4.1 Investigational Product Packaging and Storage

The Sponsor or designee will provide the Investigator with:

- packaged ARCT-154 containers labeled in accordance with specific country regulatory requirements.
- sodium chloride intended for use as diluent and placebo will be provided
- ChAdOx1 vaccine

See the Pharmacy Manual for additional guidance study vaccine packaging and study vaccine storage requirements.

The study staff is required to document the receipt, dispensing, and return/destruction of ARCT-154 and ChAdOx1 supplies provided by the Sponsor or designee. The study center must destroy or return for destruction all unused frozen vials of ARCT-154/ ChAdOx1 to the Sponsor or designee. Vials of ARCT-154/ ChAdOx1 should be destroyed by the study center or delegate **only** after drug accountability has been done by the unblinded study monitor. Destruction or return of study vaccine must be documented.

6.4.2 Clinical Supplies for Reconstitution and Administration of Study Vaccine

Syringes, needles and filters will be supplied by the Sponsor or designee. See the Pharmacy Manual for guidance on the use of ancillary supplies for vaccinations.

6.4.3 Study Vaccine Accountability

The investigator will maintain accurate records of receipt of all study vaccines (ARCT-154, placebo/diluent, ChAdOx1), including dates of receipt. In addition, accurate records will be kept regarding when and how much study vaccine is administered to each participant in the study. Only participants enrolled in the study may receive any study vaccine and only authorized site personnel may supply or administer the study vaccine. Reasons for departure from the expected dispensing regimen must also be recorded. At the completion of the study, to satisfy regulatory requirements regarding drug accountability, all study vaccines will be reconciled and destroyed according to applicable regulations. Further guidance and information for the final disposition of unused study vaccines are provided in the Pharmacy Manual.

6.4.4 Other Supplies for Participant Use

Study sites will distribute sponsor-provided thermometers (for body temperature measurement) and rulers to measure injection site erythema and induration/swelling reactions, respectively. The measurements will be captured in the Diary provided by the site. Electronic Diaries will be used wherever possible and, if a participant does not have his/her own smart phone devices for eDiary use, the site will provide an electronic alternative or a paper diary.

If the participant should have suspected or confirmed COVID-19 and cannot come into the clinic for evaluation, the participant may undergo a telemedicine or Home Visit.

6.5 Overdose Management

Study vaccine (ARCT-154, placebo or ChAdOx1) errors (including overdose, underdose, and administration error) must be documented as protocol deviations. A brief description should be provided of the deviation, including whether the participant was symptomatic (list symptoms) or asymptomatic, and whether the event was accidental or intentional.

Dosing details should be captured on the Dosing eCRF.

An overdose is the accidental or intentional administration of a vaccine in an amount higher than the dose being studied. An overdose or incorrect administration of study vaccine is not itself an AE, but it may result in an AE. If the participant receives a dose of study vaccine (ARCT-154,

placebo or ChAdOx1) that exceeds protocol specifications and the participant is symptomatic, the symptom(s) should be documented as an AE.

Should an overdose occur, the investigator or designee should contact the CRO medical monitor or designee within 24 hours.

There are no known treatments for potential overdose of study vaccine. In the event of an overdose, the individual should be monitored and provided with symptomatic treatment as appropriate.

Unless there is a user error leading to failure to administer any volume of study vaccine, “catch-up” vaccine administrations will not be performed.

6.6 Blinding

The study vaccines will be administered in an observer-blind fashion.

Each of the study vaccines will be prepared by an unblinded trained team member and in accordance with the Pharmacy Manual.

Unblinded personnel (of limited number) will be assigned to vaccine accountability procedures and will prepare study vaccine for all participants. These personnel will have no study functions other than study vaccine management, documentation, accountability, preparation, and administration. They will not be involved in participant evaluations and will not reveal the identity of study vaccine to either the participant or the blinded study site personnel involved in the conduct of the study unless this information is necessary in the case of an emergency.

- Unblinded health care providers will administer the study vaccine. They will not be involved in assessments of any study endpoints.
- All documents containing unblinded information must also be kept out of view of the blinded team members and the study participants.
- Unblinded site monitors not involved in other aspects of monitoring will be assigned as the study vaccine accountability monitors. They will have responsibilities to ensure that sites are following all proper study vaccine accountability, preparation, and administration procedures.
- An unblinded DSMB will perform the ongoing review of safety data from enrolled participants to determine if there are any unexpected risks that warrant modification or termination of the study. The DSMB will provide recommendations to the Sponsor following each data review.

In order to maintain an observer-blind design, investigators, site staff, participants, and CRO staff with oversight of study conduct will remain blinded to vaccine assignments for the study duration. The Sponsor representatives with direct oversight of the study will remain blinded to individual participant vaccine assignments until the time of study unblinding at the final analysis. The Switchover/Further Study Vaccine will occur in a blinded fashion and participants and blinded site and Sponsor personnel will remain blinded to treatment assignment until End of Study (EOS).

Additional members of the Sponsor team that are not involved in direct oversight of the study may receive unblinded study data but will not share any unblinded information with the Sponsor team overseeing the study. Sponsor staff and other persons that will become unblinded at the various data analysis time points will be specified in a written unblinding plan prior to unblinding occurring.

The dosing assignment will be concealed by having the unblinded personnel prepare the study vaccine in a secure location not accessible or visible to blinded study staff members. Only delegated unblinded site staff will perform the injection of prepared study vaccine. Once the injection is completed, only the blinded study staff will perform further assessments and interact with the participants. Access to the randomization code will be strictly controlled at the pharmacy. All other site staff performing study-related assessments will be blinded for the duration of the study.

6.6.1 Breaking the Blind

An individual participant's study vaccine assignment will not be unblinded to the investigator or other blinded study site staff until the EOS unless awareness of the vaccine assignment is relevant to the care of the study participant. If the blind needs to be broken because of a medical emergency, the investigator may unblind an individual participant's treatment allocation.

To the extent possible before unblinding, the investigator should contact the medical monitor to discuss the medical emergency and the reason for revealing the actual treatment received by that participant. The study vaccine assignment will be unblinded through IRT. Reasons for unblinding must be clearly explained and justified in the eCRF. The date on which the code was broken together with the identity of the person responsible must also be documented.

Participants who choose to receive vaccination with licensed COVID-19 vaccine will be encouraged to remain in the study, but those that choose to leave the study to pursue alternate vaccination will not be unblinded to study treatment unless there is an unexpected post study SAE attributed as related to study vaccine by the study investigator.

6.7 Compliance With Study Treatment

When participants are dosed at the site, they will receive the study vaccine directly from the Investigator or designee under medical supervision. The date and time of each dose administered in the clinic will be recorded in the source documents and recorded in the eCRF. The receipt of study vaccine and study participant identification will be confirmed at the time of dosing by a member of the study site personnel other than the person administering the study vaccine.

6.8 Concomitant Therapies and Procedures

6.8.1 Concomitant Therapy

Study site staff must question the participant regarding any medications taken (including herbal/homeopathic substances) and vaccinations received by the participant. The following information will be recorded in the eCRF:

- All non-study vaccinations administered within the period starting 28 days before the first dose of study vaccine and for the duration of study participation.
- All concomitant medications and non-study vaccinations taken through 28 days after each study vaccination.
- Any concomitant medications/vaccines used to prevent or treat COVID-19.
- Any concomitant medications/vaccines relevant to or for the treatment of a solicited or unsolicited AE, an SAE, an MAAE, or an AE leading to discontinuation/withdrawal.
- Participants will be asked prior to vaccination and will be asked for 7 days after each vaccination of the initial series in the Diary if they have taken any antipyretic or analgesics to prevent or treat vaccine-associated side effects (AEs). For participants in Phase 2/3a, the diary will also be completed for 7 days after the 3rd dose of study vaccine (Day 92).

All medications and interventions necessary for the appropriate care of the study participant, particularly to treat COVID-19, should be administered and appropriately documented along with the AE.

All concomitant medications/vaccines must be recorded in the eCRF until 28 days after each dose of study vaccine. Thereafter, only vaccines and concomitant medications associated with an SAE, MAAE, or AEs leading to discontinuation/withdrawal will be entered in the eCRF.

Prohibited Concomitant Vaccines

Receipt of off-study COVID-19 vaccine is actively discouraged for enrolled participants. Any participant who receives an off-study COVID-19 vaccine will not receive further study vaccinations. All participants should remain in the study until the Final Visit (Day 394). If the off-study vaccine becomes known to the site prior to Switchover/Further Study Vaccine, the participant will not receive Switchover/Further Study Vaccine vaccinations and will be requested to stay in the study through Final Visit (Day 394).

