4.4 Study Design

This is a Phase 1/2/3, randomized, controlled, observer-blind study designed to evaluate the safety, immunogenicity and efficacy of ARCT-154 in adult participants to be enrolled in Vietnam. This study design has been updated to include a cohort (Phase 3c) to evaluate the immunogenicity, safety, and efficacy of ARCT-154 versus a comparator COVID-19 vaccine.

The study is divided into five parts: Phase 1, Phase 2, Phase 3a, Phase 3b and Phase 3c.

Participants in Phase 1 and 3b will be randomly assigned (Section [4.5.2](#)) to a study group that will receive up to 2 vaccination series (4 doses of study vaccine total). Each vaccination series comprises two vaccinations at 28-day intervals: an initial vaccination series with vaccinations on Day 1 and Day 29 and an additional two-dose vaccination series with the opposite vaccine at the 6-month timepoint on Day 92 and 120, which is at the 2-months after the second dose (referred to as the “Switchover” vaccination series throughout the protocol). Each participant in Phase 1 and 3b is planned to receive a two-dose vaccination series of ARCT-154 at a dose of 5 µg and a

two-dose vaccination series of placebo (saline). Therefore, the study group participants that initially received two doses of ARCT-154 will receive two doses of placebo on Switchover and study group participants that initially received placebo will receive two doses of ARCT-154 5 µg on Switchover (Figure 1).

Participants in Phase 2 and 3a will be randomly assigned to a study group that will receive two vaccinations with either ARCT-154 or placebo at a 28-day interval with vaccinations on Day 1 and Day 29. With protocol version 8.0, participants that received ARCT-154 in the initial two-dose vaccination series will be further randomized to receive either ARCT-154 or placebo (in a 3:1 ratio) at Day 92 (referred to as “Further Study Vaccine” throughout the protocol) followed by placebo at Day 120. Participants that received placebo in the initial vaccination series will undergo Switchover to receive ARCT-154 at Day 92 and Day 120.

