PP immunogenicity sets will be derived up to the analysis time point concerned based on the availability of each assay. Three time points are considered:

- Up to Day 57
- Up to Day 92
- Up to Day 120

The following major protocol deviations are expected to affect efficacy and will lead to exclusion of a participant from the PP efficacy set:

- Received wrong study vaccine up to Day 92
- Did not receive study vaccine
- Received non-study COVID-19 vaccine (IcEv2) up to Day 92
- COVID-19 infection (positive RT-PCR or other COVID-19 test) up to Day 36
- Result of SARS-CoV-2 anti-nucleocapsid antibodies test is Positive/Undetermined up to Day 36

The following major protocol deviations are expected to affect immunogenicity and will lead to exclusion of a participant from the PP immunogenicity sets:

- Received wrong study vaccine up to the time point concerned
- Did not receive study vaccine
- Received non-study COVID-19 vaccine (IcEv2) up to the time point concerned
- Received confounding medication (IcEv5) up to the time point concerned
- COVID-19 infection (positive RT-PCR or other COVID-19 test) up to Day 57
- Result of SARS-CoV-2 anti-nucleocapsid antibodies test is Positive/Undetermined up to Day 57

All major protocol deviations listed above are conditions leading to exclusion from the PP set specified in the protocol.

- **Immunogenicity Analysis Set (IAS):** Includes all participants who received all protocol-required doses of study vaccine (ARCT-154 or placebo) up to the evaluation timepoint concerned, who have no evidence of prior SARS-CoV-2 infection (no positive RT-PCR or other COVID-19 test or seropositivity for anti-nucleocapsid antibody) up to Day 57 and who have at least 1 valid post-vaccination immunogenicity assay result.

All participants in the IAS will be analyzed according to which study vaccine was assigned.

IAS are defined for the following Phases of the study:

- Phase 1 IAS: this corresponds to data from participants in Phase 1
- Phase 2/3a IAS: this pools data from participants in Phase 2 and 3a
- Phase 1/2/3a IAS (or phase 1/2 IAS): this pools data from Phase 1, 2 and 3a participants and will include evaluations of immunogenicity up to Day 92 only. Of note, this analysis set may be restricted to Phase 1 and Phase 2 participants for analyses on parameters not collected for phase 3a participants.

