## 6.2.7 Intercurrent Events

**Table 5 Intercurrent Events**

Label	Intercurrent Event (IcEv) Type
IcEv1 (Death not due to COVID-19)	Death due to any cause other than COVID-19 associated.

IcEv2 (Non-study COVID-19 vaccine)	Use of non-study COVID-19 vaccine.
IcEv3 (Early infection)	Positive reverse transcriptase-polymerase chain reaction (RT-PCR) test or other COVID-19 positive test or seropositivity for anti-nucleocapsid antibody indicating exposure to SARS-CoV-2 prior to vaccination or SARS-CoV-2 infection prior to 7 days (inclusive) after the second study vaccination dose (Day 35).
IcEv4 (Study infection)	Develops virologically confirmed SARS-CoV-2 infection, with or without COVID-19 symptoms (Positive RT-PCR or other COVID-19 positive test or seropositivity for anti-nucleocapsid antibody indicating exposure to SARS-CoV-2) more than 7 days after second study vaccine dose ( $\geq$ Day 36). Additional details on how to define primary efficacy endpoint is presented in Section 6.4.
IcEv5 (Confounding On-study Medications)	Receives any of the following concomitant medications/vaccines prior to the time point for which the analysis is being performed: 
 
• Live vaccines within 28 days before or after any study vaccination
 
• Systemic (oral, intravenous, intramuscular or subcutaneous) corticosteroids given at any study time point prior to the timepoint at which the analysis is being performed
 
• Blood products or immunoglobulins given at any study time point prior to the timepoint at which the analysis is being performed
 
• Immunosuppressive medications, including cytotoxic medication for cancer or autoimmune disease, given at any study time point prior to the timepoint at which the analysis is being performed
 

Abbreviations: COVID-19=coronavirus disease 2019; IcEv=intercurrent event; SARS-CoV-2=severe acute respiratory syndrome coronavirus 2.

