Exploratory 4b	COVID-19 with onset at any time after the first dose of study vaccine administration and up to Day 92	ITT + no prior infection (3b & Pooled)	[Last date at risk – Date received 1st dose]+1	No
Exploratory 5a	Severe COVID-19 with onset between Day 36 and Day 92 by specific variant	miITT (3b & Pooled)	[Last date at risk – Date received 1st dose]+1	No
Exploratory 5b	Severe COVID-19 with onset at any time after the first dose of study vaccine administration and up to Day 92	ITT + no prior infection (3b & Pooled)	[Last date at risk – Date received 1st dose]+1	No

\*COVID-19 events will be confirmed, protocol-defined cases. \*\* Where the last date at risk will be defined as COVID-19-event date or censor date, whichever comes first.

(a) Unless specified otherwise, reference to the protocol endpoints is a reference to the Phase 3b endpoints.

Confirmed, protocol-defined COVID-19 cases will be determined by case report form (CRF) data, as confirmed by the blinded Independent Adjudication Committee and adjudicated for severity, with the date of case onset as date of symptom onset and date of positive COVID test date, whichever occurs first. Both protocol-defined and (protocol-defined) severe cases flagged in the CRF will be included in the primary endpoint.

For participants with no covid-event during the time interval the censor date for the last date at risk is whichever of the following comes first:

- Date of completion of Day 92 visit;
- Date of death unrelated to COVID-19;
- Date of receipt of Switchover or receipt of non-study COVID-19 vaccine
- Lost to Follow-up (last known alive date or date of Day 1+91 days, which is earlier).

Section 9.2.2 presents the endpoints and analyses in terms of estimands for primary, secondary and exploratory efficacy analyses.

As a sensitivity analysis of the primary endpoint (Phase 3b only), severe cases and deaths due to COVID-19 will be repeated using all COVID-19 cases from CRF, including those cases that are not confirmed by the blinded Independent Adjudication Committee and with severe or death severity as reported in the CRF.

Day 36 is defined as second dose+7 days (29+7=36 days), and Day 92 is defined as second dose+63 days (29+63=92 days). Another sensitivity analysis of the primary endpoint (Phase 3b only) will be performed using Day 92 visit instead of second dose+63 days.

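### Protocol 6.8.1 stops eCRF entry of unlinked medications after Day 57, which blocks part of the IcEv5 exclusion of Day 92 titres, and its wording on vaccines contradicts itself

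*Protocol*

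**What the plan says.** Protocol 6.8.1 opens with a list of what goes into the eCRF. It includes "All non-study vaccinations administered within the period starting 28 days before the first dose of study vaccine and for the duration of study participation" and, with no time limit, "Any concomitant medications/vaccines used to prevent or treat COVID-19". It also asks for products relevant to an AE. A later paragraph gives a general rule, "All concomitant medications/vaccines must be recorded in the eCRF until 28 days after each dose of study vaccine", and closes with "Thereafter, only vaccines and concomitant medications associated with an SAE, MAAE, or AEs leading to discontinuation/withdrawal will be entered in the eCRF".

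The SAP contains the analyses that depend on these records:

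- Table 5 (section 6.2.7) defines IcEv5. It counts systemic "corticosteroids given at any study time point prior to the timepoint at which the analysis is being performed", with parallel entries for blood products, immunoglobulins and immunosuppressants.
- Section 6.5 drops a participant's titres after IcEv5 or after a non-study COVID-19 vaccine (IcEv2).
- Section 4.1 lists "Received confounding medication (IcEv5) up to the time point concerned" among the reasons for leaving the per-protocol immunogenicity sets.
- Section 6.4 ends time at risk for efficacy at, among other dates, "Date of receipt of Switchover or receipt of non-study COVID-19 vaccine".

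**The concern.** An exclusion can act only on exposures that are in the database. IcEv5 looks back over the whole study, but entry of medications with no link to an SAE, MAAE or discontinuation AE is required only in the 28 days after a dose. If a site follows the closing sentence, someone who takes a listed drug between two such windows keeps a titre that the plan says should come out. SAP 4.2 makes the dependence direct: per-protocol exclusions are re-programmed from the locked EDC data, and no other source is named. Immunosuppressants would tend to lower a titre, while immunoglobulins or blood products could raise it, so the direction of any distortion is not fixed.

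For vaccines, one section gives the site two different instructions about a date that determines both the IcEv2 titre exclusion and the end of time at risk for the primary efficacy endpoint.

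**Working it through.** No power or alpha figure is involved. The check is day arithmetic, followed by setting the rules side by side.

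**1. Recording windows.** Protocol 4.4 gives "an initial vaccination series with vaccinations on Day 1 and Day 29", with the next dose on Day 92. Section 6.8.1 gives 28 days of routine entry after each dose.

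- After dose 1: 1 + 28 = Day 29, when dose 2 opens a new window.
- After dose 2: 29 + 28 = Day 57.
- Days outside any window before Day 92: Days 58 to 91, or 91 − 57 = 34 days. That is 34/91 = 37% of the look-back from Day 1 to the Day 92 draw.
- Day 92 visit at the end of its window (Appendix 1): +14 days in Phase 2/3a gives 105 − 57 = 48 days; +30 days in Phase 1 gives 121 − 57 = 64 days.
- For a participant who gets no further study vaccine, the window does not reopen.

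**2. Titres affected.** The primary Phase 1/2/3a endpoint is at Day 57, where routine entry is still running on the nominal schedule, so it is not affected. SAP Table 7 places Day 92 sVNT and binding antibody under a secondary endpoint and Day 92 MNT under exploratory ones. The Day 120 results are exploratory. SAP 6.5 calculates no p-values for immunogenicity.

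**3. Exposures affected.** A drug already in use by Day 57 has been recorded and triggers IcEv5 from then on. A drug linked to an SAE, MAAE or discontinuation AE is recorded throughout. What remains is a listed drug newly taken in Days 58 to 91 without such a link.

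**4. Whether the Day 92 eligibility review closes the gap.** Protocol 5.1.5 asks about these drugs in order to decide on further study vaccine.

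- Day 92: participants who are refused still attend (4.5.3), blood is drawn from all Phase 1/2/3a participants (4.5.5.3), and the two-dose immunogenicity set needs only the first two doses (SAP Table 7, note a). Their Day 92 titre stays in unless IcEv5 is recorded.
- Day 120: the three-dose set requires the third dose, so refused participants drop out. The exception is a steroid course under 14 days, which 5.1.5 passes to the 28-day deferral in 5.2.1. Since 64 + 28 = 92, a short course that ended by Day 64 does not even delay the Day 92 visit. That participant can contribute a Day 120 titre with an unrecorded IcEv5.

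**5. Vaccines.** Two bullets require entry of every non-study vaccination during participation and of any COVID-19 preventive product. The closing sentence, on its plain reading, limits vaccines after 28 days to those tied to an SAE, MAAE or discontinuation AE. Of the products at issue, only the non-study COVID-19 vaccine is a censoring event for efficacy (Protocol Table 18; SAP 6.4). IcEv5 drugs are handled there by treatment policy (SAP 9.2.2). Efficacy therefore needs vaccine dates only, and the bullets do ask for them.

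**The case against.** The residual medication gap may be small. An MAAE is any AE leading to unscheduled contact with a healthcare provider, telemedicine included (Protocol 7.4.1.1.4), so most infusions, injections and new prescriptions for illness would be linked and entered. This stands and limits the number of missed courses, but it does not reach use outside such a contact.

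A further bullet in 6.8.1 covers products used for any unsolicited AE with no stated time limit, and Protocol 4.5.5.2 has unsolicited AEs recorded to the Final Visit. Against this, 7.4.1.3 stops non-serious unsolicited AEs at 28 days, and the closing sentence of 6.8.1 is restrictive. The bullet is one more passage to reconcile, and it cannot help where the drug was not given for an AE.

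The weekly calls on Days 64, 71, 78 and 85 and the Day 92 visit ask about medications and vaccines. That is true, and it is what makes a remedy feasible, but 6.8.1 decides what is entered. The eligibility review does protect most of the Day 120 analysis, and that is conceded above.

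The closing sentence could also be read as leaving vaccines unrestricted and attaching the AE condition to medications alone. If that was meant, the vaccine conflict disappears. A site cannot be sure of it, and the medication gap is unchanged.

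A reader might go further and infer that outside COVID-19 vaccination goes unrecorded for 34 days of the primary efficacy window, so that vaccine efficacy is biased. The documents do not support this. Two bullets in the same section require those entries, and outside vaccination also comes up in the counselling described in 5.2.3 and the Day 92 review in 5.1.5. Any bias figure would have to assume that sites disregarded both bullets, so none is given.

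**Conclusion.** The point holds in two parts. First, the closing rule of 6.8.1 prevents full application of IcEv5 to Day 92 titres: unlinked use of a listed drug newly taken in Days 58 to 91 is not entered (34 days nominally; up to 48 in Phase 2/3a and 64 in Phase 1). The same applies to Day 120 titres only for short steroid courses compatible with the Day 92 dose. Second, 6.8.1 contradicts itself on non-study vaccines, whose dates are needed for IcEv2 and for primary-endpoint censoring. That is a conflict to reconcile, not an absence of coverage.

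This rests on three assumptions: dose 2 is given on Day 29, sites follow the closing sentence, and IcEv5 is derived from EDC data. The documents give no frequency for such exposures and no effect on titres, so the impact cannot be quantified. It is confined to secondary and exploratory immunogenicity results and is probably modest. It still merits correction, because the plan cannot otherwise carry out its own exclusion as written.

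**What to change.** Amend the closing sentence of Protocol 6.8.1 so that, after the 28-day window:

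- all non-study vaccines are entered with dates through the Final Visit;
- every IcEv5 drug class (systemic corticosteroids, immunosuppressants, blood products, immunoglobulins) is entered with dates through the last analysed titre, meaning Day 92, or Day 120 for Phase 2/3a, whether or not linked to an AE;
- other medications stay restricted as now.

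The wording costs one sentence, since the calls and visits already ask the question.

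For this trial the visits concerned have passed. SAP 2.5 states that by the January 2023 data cut all Phase 1/2/3a/3b participants had at least six months of follow-up after dose 2 or had left. The practical step is therefore to take IcEv5 dates for Days 58 to 91 from the source records of those calls and visits before database lock. The planned Phase 1/2/3a total is 100 + 300 + 600 = 1,000 participants. Sites should also confirm that non-study vaccines were entered as the bullets require. If this is not done, the SAP and study report should state that IcEv5 capture after Day 57 is incomplete and that the Day 92 and Day 120 exclusions rest on partial data.
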